7.2.9 Immunogenicity of Ibalizumab

Blood samples will be collected to test for the development of antibodies against ibalizumab at Day 0, EOS, Early Withdrawal, and other defined visits. Samples will be collected prior to ibalizumab infusion if an infusion is scheduled for that visit. The incidence of anti-ibalizumab antibody production will be determined using a validated enzyme-linked immunosorbent assay (ELISA) that has been validated for the detection of anti-ibalizumab antibodies in human serum even if circulating drug is present. Additional samples may be collected when clinical observations suggest the possibility of a clinically significant anti-ibalizumab immune response (e.g., allergic response, serum sickness, low drug levels, and/or loss of virologic response).

8. Adverse Events

8.1 Definitions

Per the FDA regulations in 21 CFR 312.32, the following definitions apply to this protocol:

Adverse Events. An AE is defined as any untoward medical occurrence associated with the use of a drug in humans, whether or not considered drug related.

Adverse Reaction. Any AE caused by a drug.

Treatment-Emergent AEs. A TEAE is defined as any event not present before exposure to study drug or any event already present that worsens in either intensity or frequency following exposure to test medication.

Serious Adverse Event or Serious Suspected Adverse Reaction. An AE or suspected adverse reaction is considered “serious” if, in the view of either the investigator or Sponsor, it results in any of the following outcomes: death, a life-threatening AE, inpatient hospitalization or prolongation of existing hospitalization, a persistent or significant incapacity or substantial disruption of the ability to conduct normal life functions, or a congenital anomaly/birth defect. Important medical events that may not result in death, be life-threatening, or require hospitalization may be considered serious when, based upon appropriate medical judgment, they may jeopardize the patient or subject and may require medical or surgical intervention to prevent one of the outcomes listed in this definition.

Suspected Adverse Reaction. A suspected adverse reaction means any AE for which there is a reasonable possibility that the drug caused the AE. For the purposes of IND safety reporting, “reasonable possibility” means there is evidence to suggest a causal relationship between the drug and the AE.

Unexpected Adverse Event or Unexpected Adverse Reaction. This term refers to an AE or adverse reaction that is not listed in the investigator’s brochure or is not listed at the specificity or severity that has been observed.

8.2 Eliciting Adverse Event Information

At every study visit, patients will be asked a standard, nondirective question, such as “How have you been feeling since your last visit?” to elicit any medically related changes in their well-being. They will also be asked if they have been hospitalized, had any accidents, used any new medications, or changed concomitant medication regimens (both prescription and over-the-counter medications).

In addition to patient self-report, AEs will be documented from clinically significant findings resulting from abnormal laboratory test values, physical examination findings, or other documents that are relevant to patient safety.

8.3 Reporting Adverse Events

The investigator is responsible for reporting to the Sponsor or designee all AEs that are observed or reported by the patient during the study (from the time the patient signs informed consent until 30 days after the last dose of study medication is given), regardless of their relationship to study drug or their clinical significance. Patients will be instructed to contact study site personnel at any time after informed consent if any symptoms develop.

To ensure compliance with FDA regulations (21 CR 312.64), site investigators must immediately report to the Sponsor all AEs that meet the SAE criteria, regardless of presumed relationship to the investigational agent. The Sponsor will carefully review the SAE information to monitor the investigational drug's toxicity profile and patient safety. If any event meets the FDA's reporting criteria, it will be submitted to the FDA as an IND Safety Report (21 CFR 312.32).

Recording of AEs will begin after study drug is first administered. Any untoward medical condition that occurs after the informed consent is signed but before the first administration of the study drug will be recorded as medical history, unless it is related to a study procedure. AEs will be recorded from the first dose of study medication and until 30 days after the last dose of study medication, regardless of its relationship to study drug. AEs will be documented in the patient's source documents and recorded in the AE section of the EDC system.

All AEs reported or observed during the study must be recorded in detail in the AE section of the EDC system and followed to a satisfactory resolution or until the Principal Investigator deems the event to be chronic or the patient to be stable.

Information to be collected includes the event term, date of onset, date of resolution, Investigator-specified assessment of severity and relationship to study drug, and seriousness, as well as any required treatment or evaluations and outcome.

Pre-existing conditions (present before the start of the AE collection period) are considered concurrent medical conditions and should NOT be recorded as AEs. However, if the pre-existing condition worsens in severity, the investigator must report it as an AE.

Each AE should be recorded to represent a single diagnosis. Accompanying signs (including abnormal laboratory values) or symptoms should NOT be recorded as additional AEs. If a diagnosis is unknown, sign(s) or symptom(s) should be recorded as an AE(s). Changes in laboratory values are only considered to be AEs if they are judged to be clinically significant (i.e., if some action or intervention is required or if the investigator judges the change to be beyond the range of normal physiological fluctuation). If abnormal laboratory values are the result of pathology for which there is an overall diagnosis (e.g., increased creatinine in renal failure), the diagnosis only should be recorded as an AE.

Pre-planned procedures (surgeries or therapies) that were scheduled prior to the start of AE collection are not considered AEs. However, if a pre-planned procedure is performed early (e.g., as an emergency) due to a worsening of the pre-existing condition, the worsening of the condition should be captured as an AE. Elective procedures performed where there is no change in the patient's medical condition should not be recorded as AEs, but should be documented in the patient's source documents.

The Medical Dictionary for Regulatory Activities (MedDRA) and WHO Drug Dictionary (WHODD) will be used to code all AEs and classify all medicines, respectively. All coding will be performed by Westat and will be reviewed and approved by the medical monitor.

All AEs, whether serious or not, should be followed to a satisfactory resolution or until the Principal Investigator deems the event to be chronic or the patient to be stable and the AE is determined to be not clinically significant.

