
Safety and Effectiveness Assessments:
	
Primary safety and effectiveness variables:
 
Cohort 1 and Cohort 2
 
 ■ Safety and tolerability of ibalizumab as assessed by AEs and Discontinuations 
Cohort 2 only
 
 ■ Proportion of patients achieving a $\geq 0.5 \log_{10}$ decrease from Baseline in viral load at Day 7 
Secondary safety and effectiveness variables:
 
Cohort 1 and Cohort 2
 
 ■ HIV-1 sensitivity/susceptibility changes associated with virologic failure after administration of ibalizumab 
Cohort 2 only
 
 ■ Proportion of patients with HIV-1 RNA levels < 50 copies/mL and < 400 copies/mL at assessment time points ■ Mean change from Baseline in viral load at Day 7 and all assessment time points ■ Proportion of patients achieving a $\geq 0.5 \log_{10}$ and $\geq 1.0 \log_{10}$ decrease from Baseline in viral load at all assessment time points

Safety Assessments:
	
Safety assessments will include the following:
 
 ■ Physical examinations ■ Vital sign measurements ■ Clinical laboratory parameters (hematology, serum chemistry, and urinalysis) ■ Monitoring of AEs and concomitant medications ■ Incidence of Class C events as defined by the CDC Classification System for HIV Infection (Appendix A) ■ Anti-ibalizumab antibody levels (immunogenicity of ibalizumab)

Statistical Considerations:	
Sample Size: A sample size of approximately 100 patients is anticipated to be enrolled, though the number of participating patients will not be limited and may exceed 100. The analysis of study data will be primarily descriptive, with emphasis on tabular and graphical displays. Summary descriptive statistics will be calculated along with point and interval estimates of AEs.
 
Effectiveness: (Cohort 2 only) The primary effectiveness endpoint of the study is the proportion of patients achieving a $\geq 0.5 \log_{10}$ decrease from Baseline in viral load at Day 7.
 
Safety Analyses: The safety analyses will include descriptions of treatment-emergent AEs (TEAEs), Class C events per the CDC Classification System for HIV Infection, clinical laboratory test results, physical examination findings, vital sign results, and immunogenicity of ibalizumab.

------------------------------------	---

ABBREVIATIONS

ABBREVIATION	TERM
AE	adverse event

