8.4 Assessment of Causality

The investigator's assessment of an AE's relationship to study drug is part of the documentation process, but it is not a factor in determining what is or is not reported in the study. If there is any doubt as to whether a clinical observation is an AE, the event should be reported.

The relationship or association of the study drug in causing or contributing to the AE will be characterized by the investigator using the following classifications and criteria:

Unrelated. This relationship suggests that there is no association between the study drug and the reported event. To be deemed unrelated, an alternative etiology must be present.

Possible. This relationship suggests that treatment with the study drug caused or contributed to the AE. That is, the event follows a reasonable temporal sequence from the time of drug administration and/or follows a known response pattern to the study drug, but could also have been produced by other factors.

Probable. This relationship suggests that a reasonable temporal sequence of the event with drug administration exists and—based upon the known pharmacological action of the drug, known or previously reported adverse reactions to the drug or class of drugs, or judgment based on the investigator’s clinical experience—the association of the event with study drug administration seems likely.

Definite. This relationship suggests that a definite causal relationship exists between the drug administration and the AE and that other conditions (concurrent illness, progression/expression of disease state, or concurrent medication reaction) do not appear to explain the event.

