#### 4.3.2. **AEs**

All AEs will be coded, using MedDRA dictionary version 17.0. The use of another version will not be considered a violation of the SAP, nor require an amendment to the plan. All summary tables will be based on coded preferred terms (PTs), instead of verbatim terms. The only exception being all rashes are combined into one category named RASHES. The categories and definitions of severity and causal relationship for all AEs, including the criteria for which an AE is to be classified as "serious," are as described in the protocol (Section 8).

A treatment-emergent AE (TEAE) is defined as any event not present before exposure to study drug or any event already present that worsens in either intensity or frequency following exposure to study drug. AEs with missing start dates, but with stop dates either overlapping into the dosing period or missing, will be considered TEAEs. A TEAE with missing severity or relationship will be considered severe or related, respectively.

The overall incidence of TEAEs will be summarized for all patients in the SAF Population. The number and percentage of patients having the following will be tabulated:

- TEAE
- Serious TEAE
- TEAE leading to discontinuation
- TEAE with outcome of death
- TEAE related to study drug (definitely, probably, or possibly)

- Severe TEAE
- Class C TEAE per the Centers for Disease Control and Prevention (CDC) Classification System for HIV Infection

The overall incidence of TEAEs will also be summarized by System Organ Class (SOC), and by SOC and PT. The number and percentage of patients reporting an event, as well as the number of events reported by the patients will be tabulated. The incidence of serious TEAEs and TEAEs leading to study discontinuation (if any) will be summarized in the same manner. If there are multiple occurrences of the same TEAE within any SOC or PT for the same patient, only the first occurrence will be counted.

The incidence of TEAEs by severity/grade (mild, moderate, severe, or potentially life-threatening) and by relationship to study drug (unrelated, possibly related, probably related, and definitely related), and the incidence of SAEs by relationship to study drug, will also be summarized.

All other AEs will be classified as non-TEAEs and identified in listings only. Serious TEAEs, TEAEs leading to study discontinuation, and TEAEs with an outcome of death will be presented in separate listings, if needed.

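### The AE recording rule in Protocol 8.3 leaves out worsening in frequency, which the TEAE definition includes, so some TEAEs may go unrecorded or be recorded unevenly across sites

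*Protocol*

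**What the plan says.** **Definition.** Protocol 8.1 gives two ways for an event to be treatment-emergent. It is new after exposure, or it is "any event already present that worsens in either intensity or frequency following exposure to test medication". SAP 4.3.2 repeats the second route almost word for word: "any event already present that worsens in either intensity or frequency following exposure to study drug".

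**Recording rule.** Protocol 8.3 says that conditions present before AE collection starts "are considered concurrent medical conditions and should NOT be recorded as AEs". The next sentence gives the exception: "However, if the pre-existing condition worsens in severity, the investigator must report it as an AE". Frequency is not mentioned.

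**Use.** The Protocol Summary lists as a primary variable for both cohorts "Safety and tolerability of ibalizumab as assessed by AEs and Discontinuations". The SAP turns the AE part into tables: "The overall incidence of TEAEs will be summarized for all patients in the SAF Population".

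**The concern.** The definition used for analysis is wider than the rule that decides what enters the database. A patient who enters with occasional mild headaches and then has them much more often on drug, still mild, meets the TEAE definition. A site that follows 8.3 to the letter would leave that patient's headaches in the medical history.

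Two things are at stake. First, an omission of this kind can only lower the TEAE count, and it cannot be repaired at analysis because the SAP classifies only recorded events. Second, sites that follow 8.1 and sites that follow 8.3 would record the same clinical course differently. The documents anticipate about 40 sites (Protocol Summary) or about 50 (Protocol 5, SAP 3.1), so uneven capture is plausible.

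The symptoms most exposed are intermittent ones, and these are prominent in the safety history that the protocol gives. Section 1.2 reports diarrhea in 12% and headache in 9% of Phase 2b patients, and lists diarrhea, dizziness and nausea among the common adverse reactions in TMB-301. Those are on-study rates. They show which table rows could be affected, not how often a pre-existing symptom worsens in frequency alone.

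**Working it through.** No sample size, power or event count is involved, and the plan states no figure to reproduce. The check sets the recording rule beside the definition for a pre-existing condition after the first dose.

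**Step 1. Is severity the same thing as intensity?** Protocol 8.5, on severity, has the investigator rate the intensity of the AE on the mild to potentially life-threatening scale. The two words refer to one scale. What differs between 8.1 and 8.3 is therefore frequency.

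**Step 2. Case by case.**

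| Change after first dose | TEAE under Protocol 8.1 and SAP 4.3.2? | Recorded under the literal 8.3 rule? | Consistent? |
|---|---|---|---|
| None | No | No | Yes |
| Worse in severity only | Yes | Yes | Yes |
| Worse in severity and frequency | Yes | Yes | Yes |
| Worse in frequency only, same grade | Yes | No | **No** |

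One of the four cases conflicts.

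**Step 3. Can a frequency-only worsening still be recorded by another route?**

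- Protocol 8.4: "If there is any doubt as to whether a clinical observation is an AE, the event should be reported". This helps if the site is in doubt. A site that reads 8.3 as settling the matter has little reason to be.
- Protocol 8.3, pre-planned procedures: if a procedure is done early "due to a worsening of the pre-existing condition, the worsening of the condition should be captured as an AE". This is not limited to severity, but it applies only when a procedure is brought forward.
- Protocol 8.3, serious events: anything meeting the SAE criteria is reportable. This leaves the non-serious cases.
- Protocol 8.5, grading by functional interference: more frequent episodes may raise the grade. Severity has then worsened and 8.3 already applies. Same-grade cases remain.

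Protocol 8.5 also asks for the onset and duration of each episode of an intermittent AE, but only once the event has been accepted as an AE.

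**Step 4. What is left?** Non-serious worsening in frequency alone, at an unchanged grade, with no procedure brought forward and no doubt in the investigator's mind.

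**Step 5. Can it be sized?** The expected number missed is N × p × q × r. Here N is the number of patients treated, p the share entering with an intermittent symptom, q the share of those who worsen in frequency only, and r the share of those not captured by a route in Step 3. The documents anticipate N of about 100 (Protocol Summary, SAP 3.1) or about 50 (Protocol 5). They give none of p, q or r, so the under-count cannot be computed.

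**Step 6. Could the change be judged if it were recorded?** The items that 8.3 lists for each AE include severity but not frequency. The SAP shell for the medical history listing (16.2.4.2) shows only the condition with its start and stop dates. Nothing in these places gives a baseline frequency to compare with.

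**The case against.** The strongest counter-case is that 8.3 creates a duty to report when severity worsens but does not say that this is the only case that may be reported. The 8.1 definitions apply to the whole protocol, 8.3 itself opens by asking for all AEs whatever their clinical significance, and 8.4 resolves doubt towards reporting. A conscientious site could record a clear rise in frequency and break no rule. For some symptoms frequency may already be part of the grade; the grading table in Appendix B is not among the documents, so this cannot be settled here. Finally, the study is open-label and non-randomized, with descriptive analysis and no formal testing (SAP 2.4.2, 2.4.3, 3.4.1, 3.4.2), so no test or decision rule turns on these events.

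Much of this stands, and it limits the point. A reader might infer that frequency-only worsenings never reach the safety tables, or that sites are forbidden to enter them. The documents do not support that reading, because of the routes in Step 3. A reader might also want a rate of missed events; any such figure would be assumption from end to end.

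The mismatch itself is not answered. The specific instruction on pre-existing conditions is the one a site is most likely to apply, and none of the general clauses names frequency. The lack of a formal test does not remove the problem either, since in a descriptive safety study the incidence tables are the result.

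Cohort 1 needs separate care. These patients enter already on ibalizumab, and SAP 4.3.1 counts their exposure from the first dose in the previous study. A symptom present at entry to TMB-311 comes before AE collection here but may not come before exposure. The mismatch is clearest in Cohort 2.

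**Conclusion.** The point holds as a mismatch between collection and analysis on part of the primary safety variable. Non-serious, same-grade worsening in frequency may go unrecorded, or may be recorded at some sites and not at others, so TEAE incidence can be under-counted. To the extent that sites follow 8.3 literally, the error runs one way, towards fewer TEAEs.

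The size is unknown. It is probably modest, because only one of the four cases is affected and several routes narrow it further. That is a judgement and not a calculation. The conclusion rests on the wording of Protocol 8.1 and 8.3 and SAP 4.3.2, and on sites reading the 8.3 exception as complete. eCRF completion guidance, which is not among the documents, could reduce the problem if it already names frequency.

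**What to change.** In Protocol 8.3, extend the exception so that a pre-existing condition is reported as an AE when it worsens in severity (intensity) or in frequency, with onset at the date of worsening. Put the same wording in the eCRF completion guidance. Have sites note the baseline frequency of intermittent conditions in the medical history; without it, a change in frequency cannot be judged or checked. SAP 4.3.2 then needs no change to its definition.

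Removing frequency from the definition in both Protocol 8.1 and SAP 4.3.2 would also restore consistency. It would narrow what the study counts as treatment-emergent, so aligning the recording rule is the better choice.

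The cost is a short protocol change, a few more AE records, one small added data item, and AE rates that may look slightly less favourable. If some patients have already been followed under the present wording, the study report should say that their frequency-only worsenings may be incompletely captured.

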8.4 Assessment of Causality

The investigator's assessment of an AE's relationship to study drug is part of the documentation process, but it is not a factor in determining what is or is not reported in the study. If there is any doubt as to whether a clinical observation is an AE, the event should be reported.

The relationship or association of the study drug in causing or contributing to the AE will be characterized by the investigator using the following classifications and criteria:

Unrelated. This relationship suggests that there is no association between the study drug and the reported event. To be deemed unrelated, an alternative etiology must be present.

Possible. This relationship suggests that treatment with the study drug caused or contributed to the AE. That is, the event follows a reasonable temporal sequence from the time of drug administration and/or follows a known response pattern to the study drug, but could also have been produced by other factors.

Probable. This relationship suggests that a reasonable temporal sequence of the event with drug administration exists and—based upon the known pharmacological action of the drug, known or previously reported adverse reactions to the drug or class of drugs, or judgment based on the investigator’s clinical experience—the association of the event with study drug administration seems likely.

Definite. This relationship suggests that a definite causal relationship exists between the drug administration and the AE and that other conditions (concurrent illness, progression/expression of disease state, or concurrent medication reaction) do not appear to explain the event.

